### 8.9.6.3 Haemodynamic Assessment

**Table 39 Summary of Duplex ultrasonography (Mean Volume flow – measured in one leg) by Time and Treatment**

Time	Treatment	N	Mean	SD	Median	Min	Max
Baseline	Treatment  : NMES + EA and NMES+EA+SET	XX	XX.XX	XX.XX	XX	XX	XX
	Control  : EA and EA+SET	XX	XX.XX	XX.XX	XX	XX	XX
	Treatment  : NMES + EA and NMES+EA+SET	XX	XX.XX	XX.XX	XX	XX	XX
3 months	Control  : EA and EA+SET	XX	XX.XX	XX.XX	XX	XX	XX

The average value of the 5 readings taken from the Volume Flow for the measured in one leg by patient in the Device group is presented in the table.

Treatment: NMES + Local Available Exercise Therapy (NMES+EA and NMES+EA+SET)

 Control: Local Available Exercise Therapy (EA and EA+SET)

**Table 40 Output of Linear Regression Model for Duplex ultrasonography (Mean Volume flow – measured in one leg) at 3 months**

Variable	Coefficient	SE	t	P> t	Confidence interval
Mean-DU - VF(Baseline)	XX.XX	XX.XX	X.XX	X.XXX	X.XX
Treatment	XX.XX	XX.XX	X.XX	X.XXX	X.XX
Centre	XX.XX	XX.XX	X.XX	X.XXX	X.XX
Group	XX.XX	XX.XX	X.XX	X.XXX	X.XX
Age	XX.XX	XX.XX	X.XX	X.XXX	X.XX
Gender	XX.XX	XX.XX	X.XX	X.XXX	X.XX
BMI	XX.XX	XX.XX	X.XX	X.XXX	X.XX
_cons	XX.XX	XX.XX	X.XX	X.XXX	X.XX

R-square = X.XX Adj R-Squared=X.XX Prob>F=X.XX

Linear regression model: Mean DU -Volume flow (VF) measured in one leg at 3 months = intercept + Mean-VF (Baseline) + Treatment + Centre + Type + Age + Gender + BMI + residual error. Treatment=NMES + local available Exercise therapy vs. local available Exercise therapy only (1,0), Group= Set or Non-SET group (1,0), Centre=centre identifier.

**Table 41 Summary of Duplex ultrasonography (Mean Time Average Mean Velocity – measured in one leg) by Visit and Treatment.** Same display as Table 39, but for Duplex ultrasonography (Time average mean velocity – measured in one leg).

**Table 42 Output of Linear Regression Model for Duplex ultrasonography (Mean Time average mean velocity – measured in one leg) at 3 months.** Same display as Table 40, but for Duplex ultrasonography (Mean Time average mean velocity – measured in one leg). Linear regression model: DU – Mean Time average mean velocity (TAMV) measured in one leg at 3 months = intercept + TAMV(Baseline) + Treatment + Centre + Group + Age + Gender + BMI + residual error. Treatment=NMES + local available exercise therapy vs. local available exercise therapy only (1,0), Centre=Centre identifier, Group= Set or non-SET group (1,0) and Baseline characteristics= Age, gender, BMI, Smoking status .

Imperial Clinical Trials Unit	STATISTICAL ANALYSIS PLAN	NESIC
-------------------------------	---------------------------	-------

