**5.4 Other baseline investigations**

Imperial Clinical Trials Unit	NESIC Clinical Study Protocol V6.0 24/03/2020	Form Number CR001A-T
-------------------------------	---	-------------------------

- **Demographic information & vital signs:** age, ethnicity, date of birth, lifestyle, socioeconomic status, weight, height, blood pressure, pulse
- **Treadmill:** The Gardner-Skinner graded treadmill test will be used (15). The treadmill will start at 3.2 km/h at a 0% incline. Every 2 minutes, the gradient of the treadmill will increase by 2%. Patients will indicate the start of their claudication pain, which will be recorded as the Initial Claudication Distance (ICD) and finally stop the test at the point the patient does not want to continue due to lower limb pain; this is the Absolute Walking Distance (AWD). The patient will not be given a final score to prevent bias. If patients are able to walk for longer than 15 minutes on the treadmill, they will be excluded from the trial.
- **Quality of Life questionnaires:** The validated EuroQoL (EQ-5D-5L) questionnaire and Short Form-36 (SF-36) questionnaire will be used to assess the generic QoL and will allow economic assessment based on intervention and score improvement. The validated Intermittent Claudication Questionnaire (ICQ) will be used to assess change in disease-specific QoL. These should be completed prior to informing the participant of the treatment allocation to prevent bias.
- **Haemodynamic assessment**
  - **Duplex ultrasonography:** Using the appropriate arterial ultrasound probe and pre-set volume flow algorithms on a duplex ultrasound machine, flow within the common femoral artery (CFA), preferably of the most affected limb, will be measured, approximately 5cm below the mid-inguinal point at the groin. Measures include volume flow (VF, cc/min) and time-averaged mean velocity (TAMV, cm/s).
    - **In the control group:** only resting values will be undertaken over a 3-minute period.

Imperial Clinical Trials Unit	NESIC Clinical Study Protocol V6.0 24/03/2020	Form Number CR001A-T
-------------------------------	---	-------------------------

- **The intervention group** will have these parameters measured at rest, at 15 and 30 minutes into device use and then at 1 and 5 minutes after device cessation (16).

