- **Laser Doppler flowmetry** - The single fibre laser optical probe of the LDF machine will be positioned on the dorsal aspect of the foot using single use adhesive pads. The LDF device measures skin surface temperature and superficial skin perfusion or blood flux, as a measure of superficial skin blood flow. Once the probe is placed, measurement is continuously collected via the LDF software.
  - **In the control group:** this will be at rest for a 3 minutes duration
  - **The intervention group:** data will be collected at rest until 5 minute after device cessation.

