### 5.8.1 Summary of Visit Schedule

Visit	Screening	Baseline*	Treatment Phase 0 - 3 months	Follow-up (months) †		
	1	2		3	4	5
				3 months	6 months	12 months
Informed consent	x					
Pregnancy Test	x					
Ankle Brachial Pressure index (ABPI) / positive stress test	x			x	x	x
Edinburgh Claudication Questionnaire						
Medical History	x					
Drug history	x			x	x	x
Peripheral pulse examination	x			x	x	x
Other exclusion criteria	x					
Randomisation		x				
Demography		x				
Vital Signs		x				
Quality of life questionnaires: EQ-5D-5L /SF-36 /ICQ		x		x	x	x
Treadmill test (ICD/ AWD)		x		x	x	x
Duplex Ultrasonography		x 		x 		
Laser Doppler Flowmetry		x 		x 	x	x
NMES training		x				
SET booking		x				
Compliance Diary (SET/device/EA)		x		x		
Resources use diary		x	x	x		
Weekly text messages			x			
Data logger		x	x			
Device experience questionnaire				x		
Safety reporting			x	x	x	x

Baseline and screening visit occur on the same day if both the researcher and participant agree that informed consent has been adequately considered with time to ask questions

women of childbearing potential a required to take a urine pregnancy test

At rest and during device use in device arm

[figure not shown]
NMES treatment groups only

SET centres only

For first 3 months (treatment period) or for whole duration they are completing SET classes (whichever is longer)

[figure not shown]
 The follow up information may be collected remotely (i.e. over the telephone completely or in combination with postal questionnaires) in the event that the participant is unable to attend the appointment in the clinic or the site is unable to accommodate the onsite visit due to COVID-19.

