**Summary scores**

Physical components score (PCS)  
 Mental component score (MCS)

• Haemodynamic assessment:

- Mean values of the readings taken for the Duplex ultrasonography measure at baseline and 3 months. In the control group, only resting values will be undertaken over a 3-minute period. The intervention group will have these parameters measured at rest, at 15 and 30-minutes into device use and then at 1 and 5 minutes after device cessation [9].
  - Mean Volume Flow (VF, cc/min) for one leg (Right or Left) for each patient.
  - Mean Time average Mean Velocity (TAMV, cm/s) for one leg (right or left)
- Mean values of the readings (before use, during use and after use for the Device group and at rest for the Control group) taken for the Laser Doppler Flowmetry (LDF) measure at baseline,3,6 and 12 months
  - Mean Blood flux for one leg (Left or Right)
- Ankle Brachial Pressure Index (ABPI) measure at baseline,3,6 and 12 months for the Left and Right Ankle

• Compliance with interventions. All compliance measures below will be summarized from each participant's personalized diary.

**Supervised Exercise Therapy (SET) measured weekly from baseline to treatment, the duration of which will vary from 2 months to 6 months depending on local policy (see Appendix 3).**

Total number of weeks of exercise (summarized from each participant's personalised diary).  
 Number of therapy sessions attended each week  
 Total minutes of exercise at home each week

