**Table 43 Summary of Laser Doppler Flowmetry (Mean Blood Flux – measured in one leg) by Time and Treatment**

Time	Treatment	N	Mean	SD	Median	Min	Max
Baseline	Treatment  : NMES + EA and NMES+EA+SET	XX	XX.XX	XX.XX	XX	XX	XX
	Control  : EA and EA+SET	XX	XX.XX	XX.XX	XX	XX	XX
3 months	Treatment  : NMES + EA and NMES+EA+SET	XX	XX.XX	XX.XX	XX	XX	XX
	Control  : EA and EA+SET	XX	XX.XX	XX.XX	XX	XX	XX
6 months	Treatment  : NMES + EA and NMES+EA+SET	XX	XX.XX	XX.XX	XX	XX	XX
	Control  : EA and EA+SET	XX	XX.XX	XX.XX	XX	XX	XX
12 months	Treatment  : NMES + EA and NMES+EA+SET	XX	XX.XX	XX.XX	XX	XX	XX
	Control  : EA and EA+SET	XX	XX.XX	XX.XX	XX	XX	XX

Note: The average of the 3 reading in the Device group is presented in the table

**Table 44 Output of ANCOVA model for changes in Laser Doppler Flowmetry (Mean Blood Flux – measured in one leg) between baseline and follow up periods (3,6 and 12 months).** Same display as Table 27, but for the Laser Doppler Flowmetry (LDF) -Mean Blood Flux on one leg. ANCOVA model: Laser Doppler Flowmetry (LDF) - Mean Blood Flux in one leg at 3,6,12 months = intercept + treatment group indicator + Mean Blood Flux (Baseline). Treatment=NMES + local available exercise therapy vs. local available exercise therapy only (1,0).

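### Device-arm Duplex and laser Doppler values average resting, in-use and post-use readings against rest-only controls, so the 3-month treatment coefficient does not identify a lasting change in resting flow

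*SAP*

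**What the plan says.** **What is measured.** Protocol 5.4 has Duplex in the intervention group "measured at rest, at 15 and 30 minutes into device use and then at 1 and 5 minutes after device cessation". For laser Doppler flowmetry (LDF) in that group, "data will be collected at rest until 5 minute after device cessation". Controls have a 3-minute resting measurement only. The same scheme applies at 3 months (Protocol 5.6). The schedule footnote, "At rest and during device use in device arm", is attached to Duplex and LDF at baseline and 3 months in both documents. At 6 and 12 months, Protocol 5.6 drops Duplex and makes LDF a resting measurement for everyone.

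**What is analysed.** SAP 7.4 defines the haemodynamic endpoints as means of the readings. For LDF these are taken "before use, during use and after use for the Device group and at rest for the Control group". The note to Table 39 says that for Duplex volume flow the table presents "The average value of the 5 readings taken from the Volume Flow for the measured in one leg by patient in the Device group", and Table 41 uses the same display for time-averaged mean velocity (TAMV). The note to Table 43 says for LDF: "The average of the 3 reading in the Device group is presented in the table". That table includes 6 and 12 months.

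**The models.** Table 40 has mean volume flow "measured in one leg at 3 months = intercept + Mean-VF (Baseline) + Treatment" plus centre, group, age, gender and BMI. Table 42 does the same for TAMV. Table 44 has "Mean Blood Flux in one leg at 3,6,12 months = intercept + treatment group indicator + Mean Blood Flux (Baseline". Protocol 8.3.2 had planned multi-level regression to account for the repeated measurements.

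**The concern.** The two arms contribute different quantities under one variable name. A control value is resting flow. A device-arm value is a blend of resting flow, flow under stimulation and flow shortly afterwards. The device-arm baseline has the same blend, so the covariate already contains a response to the allocated treatment.

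Understanding mechanism is a stated secondary objective (Protocol 2.2, SAP 3.2), and SAP Table 2 marks these as the mechanistic outcomes. Two questions are of interest: whether three months of use changes resting perfusion, and what the device does to flow while it is running. The planned coefficient answers neither. A reader could take an on-device response for a three-month change in perfusion, or miss a real resting change. ABPI remains a resting between-arm comparison, but of pressure, not flow.

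**Working it through.** **Count of readings.** One at rest, two in use (15 and 30 min) and two after use (1 and 5 min) make 5, which agrees with the Table 39 note. Before, during and after make 3, which agrees with the Table 43 note. The averages therefore do include the stimulated readings.

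**What the coefficient estimates.** An ANCOVA treatment coefficient is the difference in follow-up means minus b times the difference in baseline means. Randomisation equalises expected resting flow and the other covariates. Write m0 and m3 for the control resting means at baseline and 3 months.

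- Control: baseline m0, follow-up m3.
- Device: baseline m0 + A0, follow-up m3 + D + A3.
- Coefficient: (D + A3) − b·A0.

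This equals D only if A3 = b·A0. If the acute response is stable (A3 = A0 = A), the coefficient is D + A(1 − b), so adjustment removes the acute part only when b = 1.

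**Duplex illustration.** Inputs: an 84% rise in flow (Protocol 1.6: 10 healthy people, another device, superficial femoral artery, whereas Protocol 5.4 specifies the common femoral), and post-use readings assumed back at rest. Protocol 1.8 says the effect in the device's own reports arises mainly during stimulation. In units of resting flow:

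A0 = (1 + 1.84 + 1.84 + 1 + 1)/5 − 1 = 0.336

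With D = 0 and A3 = A0, the coefficient is 0.336 × (1 − b):

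| b | 0.3 | 0.5 | 0.7 | 0.9 |
|---|---|---|---|---|
| coefficient | +0.24 | +0.17 | +0.10 | +0.03 |

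If both post-use readings stayed raised, A0 would be 0.84 × 4/5 = 0.67 and these figures would double. If A3 were half of A0, the coefficient would be 0.168 − 0.336b, from +0.07 at b = 0.3 to −0.13 at b = 0.9. That ratio is purely an assumption; it shows that the sign is not fixed.

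**LDF at 3 months.** Input: a 10-fold flux (Protocol 1.8, n = 16, healthy people), read as 10 times rest in one of three readings. A0 = (1 + 10 + 1)/3 − 1 = 3.0 times resting flux. With D = 0 and A3 = A0, the coefficient is 3.0 × (1 − b), from +2.1 to +0.3 for b from 0.3 to 0.9. With A3 half of A0 it is +0.92 to −0.25 if the rise is proportional to each patient's resting flux, and +0.6 to −1.2 if it is a fixed addition.

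**LDF at 6 and 12 months.** Follow-up is at rest in both arms, so A3 = 0 there, but the device-arm baseline is still averaged. If each visit is analysed separately, the shift is minus the fitted slope times A0.

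- Proportional rise: device-arm baseline is 4 times resting flux. With equal arms and equal resting variance V, and b now the slope of resting follow-up on resting baseline, the pooled fitted slope is (bV + 4bV)/(V + 16V) = 5b/17. The shift is −3 × 5b/17 = −0.88b, or −0.26 to −0.79 of resting flux for b from 0.3 to 0.9.
- Additive rise: −3b, or −0.9 to −2.7. This is less natural for an effect reported as a ratio.

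**With resting readings in both arms.** A0 = A3 = 0, so the coefficient is D for any b.

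**The case against.** - **Baseline adjustment deals with it.** It would if A3 = b·A0. Nothing in the documents supports that equality.
- **On-device perfusion was the intended target, and the averaging is disclosed in the table notes.** Disclosure stands, but controls have no in-use reading. The acute response is therefore a within-device-arm quantity, and a five-reading average against rest measures neither it nor the resting change.
- **The illustrative sizes do not come from this population.** This stands. They show that the coefficient cannot be interpreted, not how far it will be off. The LDF sizes in particular depend on whether the rise is proportional or additive.
- **Habituation makes a changing acute response likely.** A reader might infer this from Protocol 5.5.4. That section says only that participants may need to raise the intensity to compensate for habituation, and compensation would tend to preserve the response. The reason not to assume A3 = A0, or A3 = b·A0, is simply that no values are given.
- **No rest-versus-rest comparison exists anywhere.** A reader might conclude this too, but it goes too far. LDF follow-up at 6 and 12 months is at rest in both arms; there the defect is the baseline covariate. At 3 months the statement is correct for flow and flux.
- **The SAP schedule is weak evidence for the rest-only visits.** Agreed: its footnote 2 also sits on the treadmill row, where it makes no sense. The conclusion rests on Protocol 5.6 and 5.7.

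**Conclusion.** The structural point holds for Duplex volume flow, TAMV and LDF flux at 3 months. The coefficient is D + A3 − b·A0, and the lasting resting change cannot be recovered from it without values that the documents do not give. This does not depend on the illustrative figures.

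The Duplex illustration is +0.24 to +0.03 of resting flow with no true lasting change, assuming an 84% in-use rise, post-use readings back at rest, a stable acute response and b from 0.3 to 0.9. For LDF at 6 and 12 months, if visits are analysed separately, the averaged device-arm baseline biases the estimate downward whenever the acute rise and the slope are positive. Under a proportional 10-fold rise the shift is about −0.26 to −0.79 of resting flux. SAP 7.4 and the Table 43 note are also misworded for those visits.

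A reader might infer that the plan will overstate the device's effect, or might attach a false-positive rate to it. The documents support neither: the direction at 3 months depends on A3/A0 and b, and they give no SD, slope or evaluable number for these outcomes. The primary walking-distance endpoint, the sample size and the safety analyses are unaffected.

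**What to change.** 1. In SAP 7.4 and Tables 39 to 44, define the between-arm volume flow, TAMV and flux outcomes as the resting reading in both arms at every visit, with the resting pre-stimulation baseline reading as the covariate.
2. Report in-use and post-use readings minus rest separately, as a within-device-arm acute response at baseline and 3 months.
3. If a multi-level model is preferred, include reading phase, use the resting reading as the baseline covariate, and take the rest-phase treatment contrast as the between-arm estimate. Keeping the averaged baseline would leave a shift of −b·A0: in the Duplex illustration, −0.336 × 0.3 = −0.10 to −0.336 × 0.9 = −0.30 of resting flow. Protocol 8.3.2 specifies neither reading phase nor a baseline covariate, so the SAP would need to spell both out.
4. Correct SAP 7.4 and the Table 43 note for the rest-only LDF visits at 6 and 12 months, and state whether LDF visits are analysed separately.

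The cost is SAP wording and table shells. Resting readings are already scheduled in both arms at baseline and 3 months for Duplex and LDF, and at 6 and 12 months for LDF. The choice should be fixed before the data are seen, because a resting contrast selected afterwards would be post hoc.

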**Table 43 Summary of Laser Doppler Flowmetry (Mean Blood Flux – measured in one leg) by Time and Treatment**

Time	Treatment	N	Mean	SD	Median	Min	Max
Baseline	Treatment  : NMES + EA and NMES+EA+SET	XX	XX.XX	XX.XX	XX	XX	XX
	Control  : EA and EA+SET	XX	XX.XX	XX.XX	XX	XX	XX
3 months	Treatment  : NMES + EA and NMES+EA+SET	XX	XX.XX	XX.XX	XX	XX	XX
	Control  : EA and EA+SET	XX	XX.XX	XX.XX	XX	XX	XX
6 months	Treatment  : NMES + EA and NMES+EA+SET	XX	XX.XX	XX.XX	XX	XX	XX
	Control  : EA and EA+SET	XX	XX.XX	XX.XX	XX	XX	XX
12 months	Treatment  : NMES + EA and NMES+EA+SET	XX	XX.XX	XX.XX	XX	XX	XX
	Control  : EA and EA+SET	XX	XX.XX	XX.XX	XX	XX	XX

Note: The average of the 3 reading in the Device group is presented in the table

**Table 44 Output of ANCOVA model for changes in Laser Doppler Flowmetry (Mean Blood Flux – measured in one leg) between baseline and follow up periods (3,6 and 12 months).** Same display as Table 27, but for the Laser Doppler Flowmetry (LDF) -Mean Blood Flux on one leg. ANCOVA model: Laser Doppler Flowmetry (LDF) - Mean Blood Flux in one leg at 3,6,12 months = intercept + treatment group indicator + Mean Blood Flux (Baseline). Treatment=NMES + local available exercise therapy vs. local available exercise therapy only (1,0).

**Table 45 Summary of Right Ankle Brachial Pressure Index (ABPI) by Visit and Treatment**

Visit	Treatment	N	Mean	SD	Median	Min	Max
Baseline	Treatment  : NMES + EA and NMES+EA+SET	XX	XX.XX	XX.XX	XX	XX	XX
	Control  : EA and EA+SET	XX	XX.XX	XX.XX	XX	XX	XX
3 months	Treatment  : NMES + EA and NMES+EA+SET	XX	XX.XX	XX.XX	XX	XX	XX
	Control  : EA and EA+SET	XX	XX.XX	XX.XX	XX	XX	XX
6 months	Treatment  : NMES + EA and NMES+EA+SET	XX	XX.XX	XX.XX	XX	XX	XX
	Control  : EA and EA+SET	XX	XX.XX	XX.XX	XX	XX	XX
12 months	Treatment  : NMES + EA and NMES+EA+SET	XX	XX.XX	XX.XX	XX	XX	XX
	Control  : EA and EA+SET	XX	XX.XX	XX.XX	XX	XX	XX

**Table 46 Output of ANCOVA model for changes in Right Ankle Brachial Pressure Index (ABPI) between baseline and follow up periods (3,6 and 12 months).** Same display as Table 27, but for the Right Ankle Brachial Pressure Index (ABPI). ANCOVA model: Right Ankle Brachial Pressure Index (ABPI) 3,6,12 months = intercept + treatment group indicator + Right Ankle Index (Baseline). Treatment=NMES + local available exercise therapy vs. local available exercise therapy only (1,0).

**Table 47 Summary of Left Ankle Brachial Pressure Index (ABPI) by visit point and Treatment.** Same display as Table 45, but for the Left Ankle Brachial Pressure Index (ABPI).

**Table 48 Output of ANCOVA model for changes in Left Ankle Brachial Pressure Index (ABPI) between baseline and follow up periods (3,6 and 12 months).** Same display as Table 27, but for the Left Ankle Brachial Pressure Index (ABPI). ANCOVA model: Left Ankle Brachial Pressure Index (ABPI) 3,6,12 months = intercept +

treatment group indicator + Left Ankle Index (Baseline). Treatment=NMES + local available exercise therapy vs. local available exercise therapy only (1,0).

#### 8.9.6.4 Compliance

**Table 49 Supervise Exercise Therapy (SET) compliance information randomised patients (ITT) by treatment**

Exercise Advice - Set Centre	Treatment  : NMES + EA and NMES+EA+SET N=(XX)	Control  : EA and EA+SET N=(XX)	Total N=(XX)
Total of week recording exercises at home			
mean (SD)	XX.XX (XX.XX)	XX.XX (XX.XX)	XX.XX (XX.XX)
median (IQR)	XX.XX (XX.XX, XX.XX)	XX.XX (XX.XX, XX.XX)	XX.XX (XX.XX, XX.XX)
Total number of Therapy sessions by persons			
mean (SD)	XX.XX (XX.XX)	XX.XX (XX.XX)	XX.XX (XX.XX)
median (IQR)	XX.XX (XX.XX, XX.XX)	XX.XX (XX.XX, XX.XX)	XX.XX (XX.XX, XX.XX)
Total minutes of exercise at home at week			
mean (SD)	XX.XX (XX.XX)	XX.XX (XX.XX)	XX.XX (XX.XX)
median (IQR)	XX.XX (XX.XX, XX.XX)	XX.XX (XX.XX, XX.XX)	XX.XX (XX.XX, XX.XX)
Total minutes of therapy exercise (SET)			
mean (SD)	XX.XX (XX.XX)	XX.XX (XX.XX)	XX.XX (XX.XX)
median (IQR)	XX.XX (XX.XX, XX.XX)	XX.XX (XX.XX, XX.XX)	XX.XX (XX.XX, XX.XX)

**Table 50 Neuromuscular Electric Stimulation -compliance information randomised patients (ITT) by treatment**

Device Use Diary	Treatment  : NMES + EA and NMES+EA+SET N=(XX)	Control  : EA and EA+SET N=(XX)	Total N=(XX)
Total of days using the devices			
mean (SD)	XX.XX (XX.XX)	XX.XX (XX.XX)	XX.XX (XX.XX)
median (IQR)	XX.XX (XX.XX, XX.XX)	XX.XX (XX.XX, XX.XX)	XX.XX (XX.XX, XX.XX)
Total time on (NMES)			
mean (SD)	XX.XX (XX.XX)	XX.XX (XX.XX)	XX.XX (XX.XX)
median (IQR)	XX.XX (XX.XX, XX.XX)	XX.XX (XX.XX, XX.XX)	XX.XX (XX.XX, XX.XX)
Average - Intensity Setting			
mean (SD)	XX.XX (XX.XX)	XX.XX (XX.XX)	XX.XX (XX.XX)
median (IQR)	XX.XX (XX.XX, XX.XX)	XX.XX (XX.XX, XX.XX)	XX.XX (XX.XX, XX.XX)

